#### 4.2.1.7.2 Subgroup approach for assessing the impact of COVID-19

A supplementary sensitivity analysis method to assess the impact of the COVID-19 pandemic on PASI100 response at Week 48 will use a subgroup analysis approach and will be based on the MS. The COVID-19 pandemic subgroups are defined as:

- Week 48 visit date before COVID-19 pandemic start date (ie, prior to COVID-19 pandemic)
- Week 48 visit date on or after COVID-19 pandemic start date (ie, during COVID-19 pandemic)

Where:

- COVID-19 pandemic start date is 11 March 2020. (The date is chosen as the date the World Health Organization declared COVID-19 as a pandemic.)
- For subjects with a Week 48 visit, the actual date of the Week 48 PASI assessment will be used to determine subgroup inclusion.
- For subjects without a Week 48 visit, the scheduled Week 48 visit date will be used to determine subgroup inclusion, where:
  - Scheduled Week 48 visit date = date of first dose of study drug + 336 days.

Note:

- It is not anticipated that there will be any Week 48 visits post-pandemic for this study.
- Although the COVID-19 pandemic subgroups are determined based on an event occurring after randomization, the inclusion of a subject in the applicable subgroup is independent of their PASI assessment at Week 48 and is independent of the subject's Baseline characteristics.

This subgroup analysis for PASI100 at Week 48 will include descriptive statistics with missing data imputed using NRI.

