##### Time at risk (days)

- For all subjects, use the minimum of the following:
  - Date of last dose – date of first + 140 days.
  - Date of last clinical contact – date of first dose + 1.
  - Date of death – date of first dose + 1.

For subjects randomized to secukinumab at Baseline who initiate bimekizumab at Week 48 and continue on the same dose schedule in the OLE without switching, use the study medication duration and time at risk algorithms specified for subjects who do not switch study treatments in Section [10.1.4.1](#)

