### 10.2.1.1 COVID-19 related data considerations

In order to assess the impact of the COVID-19 global pandemic on TEAEs, an additional AE summary based on the BKZ set will be presented for the combined Initial, Maintenance, and OLE periods. The following data considerations are introduced to support this presentation by the following periods:

- Prior to COVID-19 pandemic
- During COVID-19 pandemic

The COVID-19 pandemic start date is defined as 11 March 2020 as it is the date the World Health Organization declared COVID-19 as a pandemic, see also Section 4.2.1.7.2. Note that the Week 48 and Week 96 interim analyses will be conducted during the pandemic therefore a post COVID-19 pandemic period is not defined for these analyses. If WHO declares the COVID-19 pandemic has ended prior to Week 144, then that date may be used to support presentation of a post COVID-19 pandemic period.

Where a subject's time at risk includes 11 March 2020, the subject is included in the denominator for both periods and their time at risk is split as follows:

- Prior to COVID-19 pandemic:
  - Start of time at risk to 10 March 2020
- During COVID-19 pandemic:
  - 11 March to end of time at risk

Where a subject's time at risk does not include 11 March 2020, the subject is only included in the denominator for the Prior to COVID-19 pandemic period and their time at risk would be included entirely in the Prior to COVID-19 pandemic period.

Detailed definitions for subject time at risk are outlined in Section 10.1.

AEs are assigned to the appropriate period according to start date:

- Prior to COVID-19 pandemic:

- AE start date  $\leq$  10 March 2020
- During COVID-19 pandemic:
  - AE start date  $\geq$  11 March 2020

Incidence of COVID-19 TEAEs will be summarized for the OLE treatment periods based on the OLS by treatment group.

The following PTs will be used to identify COVID-19 related TEAEs. These will include confirmed and suspected COVID-19 infection:

- Corona virus infection
- Coronavirus test positive

By-subject listings of COVID-19 TEAEs will be produced separately for OLE and OLE2 treatment periods.

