### 12.3 Appendix C: Week 96 interim analyses

An additional data cut will occur approximately after the final Week 96 visit, an interim analysis will be performed focused on the Open-Label extension treatment period.

The currently anticipated date for the final Week 96 visit is 19 March 2021. The interim analyses will include:

- Efficacy data through the Week 96 visit.
- Safety data through 19 March 2021.

Selected tables, figures and listings will be produced for this Week 96 interim analysis. Study population characteristics, demographics, other baseline characteristics and measurements of treatment compliance will be presented for the OLS. The following efficacy variables will be presented for the Open-Label extension treatment period based on the OLS, this will include presentations based on the subgroup of participants switching from secukinumab to bimekizumab:

- PASI90 response
- PASI100 response
- IGA Clear or Almost Clear (with at least a 2-category improvement from Baseline)

- IGA Clear (with at least a 2-category improvement from Baseline)
- Scalp IGA Clear or Almost Clear (with at least 2 category improvement relative to Baseline)
- Palmoplantar IGA Clear or Almost Clear (with at least a 2-category improvement from Baseline)
- DLQI total score of 0 or 1
- mNAPSI90, mNAPSI100
- Absolute, change, and percent change from Baseline in PASI score
- Absolute PASI scores of  $\leq 1$ ,  $\leq 2$ ,  $\leq 3$
- Absolute and percent change from Baseline in BSA affected by PSO
- Psoriasis BSA values of 0%,  $\leq 1\%$ ,  $\leq 3\%$
- PSD response (itch, pain and scaling)
- PSD 0 or 1 (itch, pain and scaling)
- PSD 0 (itch, pain and scaling)

The following safety variables will be presented for the Open-Label extension treatment period based on the OLS:

- Extent of exposure
- TEAEs including COVID-19 and safety topics of interest
- Laboratory data focused on TEMA and CTCAE
- e-CSSRS
- PHQ-9
- COVID-19 impact

Selected analyses of TEAEs will be presented for the subgroup of participants switching from secukinumab to bimekizumab for the Open-Label extension treatment period based on the OLS. Selected analyses of TEAEs will also be presented for the BKZ Set by treatment at the time of AE onset. These tables will include AEs from both the double-blind and Open-Label treatment period.

In addition, the following tables will be produced:

- Past psoriasis medication

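### In the supplementary COVID-19 period table, secukinumab subjects first given bimekizumab after 11 March 2020 have their time at risk counted as Prior but their adverse events as During

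*SAP*

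**What the plan says.** SAP Section 10.2.1.1 describes "an additional AE summary based on the BKZ set will be presented for the combined Initial, Maintenance, and OLE periods", with two periods, Prior to and During the pandemic. The cut is fixed: "The COVID-19 pandemic start date is defined as 11 March 2020".

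The denominator rule has two branches:
- If a subject's time at risk includes 11 March 2020, the subject counts in both periods. Time to 10 March is Prior and time from 11 March is During.
- The other branch reads: "time at risk does not include 11 March 2020, the subject is only included in the denominator for the Prior to COVID-19 pandemic period". For the person-time of such a subject the rule is the same: "their time at risk would be included entirely in the Prior to COVID-19 pandemic period".

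The numerator rule is separate: "AEs are assigned to the appropriate period according to start date". An event starting on or before 10 March 2020 is Prior. One starting on or after 11 March 2020 is During.

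Four other places fix who is in the table and when their time starts:
- Section 3.5.10: the BKZ Set includes anyone given bimekizumab in the double-blind period or in the OLE.
- Section 10.1.5.1: "For subjects randomized to secukinumab at Baseline who initiate bimekizumab at Week 48 and continue on the same dose schedule in the OLE", the Section 10.1.4.1 algorithm applies. That algorithm counts from the first OLE dose.
- Section 10.2.2: events on secukinumab are left out of the BKZ Set tables.
- Section 4.2.1.7.2: one efficacy subgroup is "Week 48 visit date on or after COVID-19 pandemic start date (ie, during COVID-19 pandemic".

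**The concern.** The second branch assumes that time at risk not containing 11 March 2020 must have finished before it. That holds for subjects randomized to bimekizumab, whose time starts at Baseline. It fails for a secukinumab-randomized subject whose first bimekizumab dose comes after the cut. That subject's bimekizumab time lies wholly after 11 March 2020, so it does not include the date, and the rule places it all in Prior. All of the subject's bimekizumab events start after the cut and are During.

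Such a subject is in the During numerator but not the During denominator, and in the Prior denominator with no possible Prior event. The exposure-adjusted incidence and event rates of Section 10.2.1 need events and time from the same period. The table exists to show whether the pandemic affected adverse event reporting, and the mismatch pushes it towards showing an effect.

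**Working it through.** The SAP gives no figure for this table, so there is none to reproduce. The check applies the rule literally.

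**1. Are such subjects expected?** Section 12.3 (Appendix C) states: "The currently anticipated date for the final Week 96 visit is 19 March 2021". Week 48 is 48 × 7 = 336 days earlier.
- 19 March 2021 − 336 days = 17 April 2020.
- 17 April 2020 − 11 March 2020 = 37 days.
- With the Section 3.1 windows (±14 days at Week 96, ±7 days at Week 48), that visit falls between 27 March and 8 May 2020, which is 16 to 58 days after the cut.

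The OLE period starts with the first dose at or after the Week 48 visit (Section 2.3.2), so first OLE doses in this interval are foreseen. A first dose on 11 March itself is handled correctly, because the time then includes the date. The affected group starts on 12 March 2020.

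**2. Are bimekizumab-randomized subjects affected?** 19 March 2021 − 96 weeks = 17 May 2019, the approximate last first dose. All of them started well before the cut, so their time either spans 11 March 2020 or ended before it. The rule works for them at subject level.

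**3. One subject.** Take a secukinumab subject with a first bimekizumab dose on 1 April 2020, dosing every 8 weeks and a last dose at Week 136, which is 88 weeks later (8 December 2021). By Section 10.1.4.1, if follow-up is complete:
- Time at risk = 88 × 7 + 140 = 756 days; 756 / 365.25 = 2.07 years.

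| | Prior (days) | During (days) | Events |
|---|---|---|---|
| SAP rule | 756 | 0 | During |
| Time placed by date | 0 | 756 | During |

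Time is shorter in some cases. A subject rolling directly into the second extension (OLE2) at Week 144 has about 96 × 7 + 1 = 673 days (1.84 years). At the Week 96 data cut of 19 March 2021, the subject above has 353 days (0.97 years).

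**4. Effect on the rates (illustration only).** The SAP gives no accrual pattern, so everything here is assumed:
- 350 bimekizumab-randomized subjects with 1.0 year Prior and 1.9 years During each;
- 300 secukinumab switchers, of whom those starting before the cut have 0.25 year Prior and 1.8 years During each;
- late switchers with 2.07 years each, all truly During.

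With k late switchers:
- true Prior = 350 × 1.0 + (300 − k) × 0.25;
- true During = 350 × 1.9 + (300 − k) × 1.8 + 2.07k;
- the rule moves 2.07k from During to Prior.

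For k = 15, true Prior = 350 + 71.25 = 421.2 and the moved time is 31.0, so the Prior rate is multiplied by 421.2 / 452.3 = 0.93. During under the rule is 665 + 513 = 1178.0, so the During rate is multiplied by 1209.0 / 1178.0 = 1.03.

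| Late share of switchers | k | Patient-years moved | Prior rate × | During rate × |
|---|---|---|---|---|
| 2% | 6 | 12.4 | 0.97 | 1.01 |
| 5% | 15 | 31.0 | 0.93 | 1.03 |
| 10% | 30 | 62.1 | 0.87 | 1.05 |
| 20% | 60 | 124.2 | 0.77 | 1.11 |

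These factors apply directly to the event rate, which divides by total time at risk. The incidence rate stops the clock at the first event, so its factors would differ in size but not in direction.

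**The case against.** The strongest reply is that this is a drafting slip in an ancillary table. The summary is descriptive, has no test, and has no place in the testing sequence of Section 4.5. The main exposure-adjusted safety tables in Section 10.2.2 are not divided by pandemic period, so their totals do not move. The label Prior, and the stated end of that period on 10 March 2020, show what was intended; a programmer might never book time from April 2020 as Prior. The same summary is also listed in Section 10.2.2 next to an Initial and Maintenance table restricted to bimekizumab-treated subjects, where the rule does no harm.

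Most of this stands and sets the severity. It does not remove the error. The text sends the time to Prior explicitly and completely, so coding it otherwise would be an undocumented departure. No other section corrects it.

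Three stronger readings are tempting but not supported:
- **That bimekizumab time after the cut is misplaced in general.** Step 2 shows that only late secukinumab switchers are affected.
- **That the patient-years moved can be stated.** A share such as 5 to 15% of 350 (about 18 to 53 subjects) has no basis in the SAP. 350 is the planned number randomized to secukinumab, the OLE is optional, and full follow-up is not assured. The 19 March 2021 date is itself only anticipated.
- **That every dosing segment starting after the cut also goes to Prior**, because the BKZ Set tables are by treatment at event onset. Section 10.2.1.1 speaks of the subject's time at risk, so this is only a possible reading.

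**Conclusion.** The rule is wrong as written for one identifiable group: secukinumab-randomized subjects whose first bimekizumab dose is on or after 12 March 2020. For them the numerator and denominator fall in different periods, and the bias always runs the same way. The group is expected on the SAP's own dates but is a tail of roughly five weeks, and its size is not given. Each member could misplace up to about 2.1 patient-years, given treatment to Week 136 and full safety follow-up. The rate factors in the illustration rest on assumed exposure and an assumed late share. They show that the effect is probably modest if the tail is small, not what it will be.

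This should be fixed before the table is used to interpret pandemic impact. It does not bear on the efficacy conclusions or on the main safety tables, so nothing supports treating it as critical.

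**What to change.** In Section 10.2.1.1, replace the sentence on time at risk that does not include 11 March 2020, and state three cases:

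- Time at risk ending on or before 10 March 2020: subject and time count in Prior only.
- Time at risk starting on or after 11 March 2020: subject and time count in During only.
- Otherwise: subject counts in both, with time split at 10/11 March 2020.

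This wording gives the right allocation whether it is applied to a subject's whole bimekizumab time or to separate dosing segments. The event rule needs no change.

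The cost is one SAP sentence and the matching line of code, with no new data. If outputs of this table already exist, check which rule was programmed and report how many subjects started bimekizumab on or after 12 March 2020.

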### 10.2.2 AE summaries

AE summaries will be provided by actual treatment at the time of the adverse event. Separate AE summaries for OLE2 treatment period will be provided by treatment sequence as specified in Section 3.6 and will be based on OLS2.

For subjects who discontinue on or prior to the final scheduled visit of the Initial Treatment Period, any AEs that emerged more than after 112 days relative to the first dose but still within the 140 days SFU window will be classified as TEAE. However, these AEs will be excluded from AE summaries based on the Initial Period but included in the AE summaries for Initial and Maintenance Treatment Period. See the description of time at risk in Section 10.1.1 for further details.

The following selected outputs will be produced for the SS for the Initial Treatment Period, for the MS for the Maintenance Treatment Period, for the SS for the Initial and Maintenance Treatment Period, for the OLS for the Open-Label Extension Period:

- Incidence of TEAEs – Overview
- Incidence of TEAEs per 100 subject years by SOC, HLT, and PT

- Incidence of Serious TEAEs per 100 subject years by SOC, HLT, and PT
- Incidence of TEAEs Leading to Discontinuation per 100 subject-years by SOC, HLT and PT
- Incidence of TEAEs by decreasing frequency of PT

The following summaries will be provided for the SS for the Initial Treatment Period, for the SS for the Initial and Maintenance Treatment Period:

- Incidence of TEAEs Leading to Death by SOC, HLT, and PT
- Incidence of TEAEs by Maximum Relationship by SOC, HLT, and PT
- Incidence of Serious TEAEs by Relationship, SOC, HLT, and PT – Note: For European Union Drug Regulating Authorities Clinical Trials (EudraCT) reporting purposes
- Incidence of Related Serious TEAEs by SOC, HLT, and PT
- Incidence of TEAEs Leading to Death by Relationship by SOC, HLT, and PT – Note: For EudraCT reporting purposes
- Incidence of TEAEs by Maximum Severity, SOC, HLT, and PT
- Incidence of TEAEs Above Reporting Threshold of 5% by SOC and PT
- Incidence of Non-Serious TEAEs by SOC, HLT, and PT
- Incidence of Non-Serious TEAEs by Maximum Relationship SOC, HLT, and PT
- Incidence of Non-Serious TEAEs Above Reporting Threshold of 5% by SOC and PT
- Incidence of Non-Serious TEAEs Above Reporting Threshold of 5% by Relationship SOC and PT
- Incidence of Related TEAEs by SOC, HLT, and PT
- Incidence of Related TEAEs Above Reporting Threshold of 5% with Risk Differences by SOC and PT

The following summary will be provided by treatment for the Initial and Maintenance Treatment Period (combined) for the SS (only subjects treated with BKZ, only Total BKZ will be summarized):

- Incidence of TEAEs per 100 subject years by SOC, HLT, and PT and by Time of Onset Relative to Anti-bimekizumab Antibody Status

Incidence of TEAEs per 100 subject years by SOC, HLT, and PT and by Time of Onset Relative to COVID-19 pandemic (prior to COVID-19 pandemic, during COVID-19 pandemic).

The following summaries will be provided by treatment for the Initial Treatment Period (SS) as well as for Initial and Maintenance Treatment Period combined (SS):

- Incidence of TEAEs Above Reporting Threshold of 5% with Risk Differences by SOC and PT
- Incidence of Serious TEAEs and Risk Differences by SOC and PT

The tables with risk differences will also be accompanied by figures (dot plots) which show the incidence of the adverse events and corresponding 95% risk difference confidence intervals. These will be ordered by descending order of risk difference (bimekizumab vs secukinumab).

The following selected AEs summaries will be provided separately for the Open-Label Extension Period. Separate AEs summaries will be provided for the OLE2 treatment period by treatment sequence as described in Section 3.6 and will be based on the OLS2:

- Incidence of COVID-19 TEAEs
- Incidence of TEAEs Overview
- Incidence of TEAEs per 100 Subject-Years
- Incidence of Serious TEAEs per 100 Subject-Years
- Incidence of Serious TEAEs by Relationship
- Incidence of TEAEs Leading to Discontinuation per 100 subject-years
- Incidence of TEAEs Leading to Death
- Incidence of Non-Serious TEAEs Above Reporting Threshold of 5% by SOC and PT
- Incidence of Non-Serious TEAEs Above Reporting Threshold of 5% by Relationship SOC and PT

In addition, the following AEs summaries will be provided for the Open-Label Extension Periods only, by treatment at the time of AE onset, and will be based separately on the OLS and OLS2.

- Incidence of TEAEs Excluding TEAEs Exclusively Related to COVID-19 Vaccine by SOC, HLT, and PT
- Incidence of TEAEs Exclusively Related to COVID-19 Vaccine by SOC, HLT, and PT
- Incidence of COVID-19 Vaccine Interval Censored TEAEs by SOC, HLT, and PT
- Incidence of COVID-19 Vaccine Interval TEAEs by SOC, HLT, and PT

The following listings will be provided separately for the OLS and OLS2:

- Listing of TEAEs Related to COVID-19 Vaccine
- Listing of COVID-19 Vaccine Interval TEAEs

The following summaries will be provided for the BKZ Set by treatment at the time of AE onset. These tables will include AEs from both the double-blind and Open-Label treatment period (excluding OLE2 treatment period). AEs that occurred while subjects received secukinumab will not be included.

- Incidence of TEAEs Overview
- Incidence of TEAEs per 100 Subject-Years
- Incidence of Serious TEAEs per 100 Subject-Years
- Incidence of TEAEs by decreasing frequency of PT

- Incidence of TEAEs per 100 subject years by SOC, HLT, and PT and by Time of Onset Relative to COVID-19 pandemic (prior to COVID-19 pandemic, during COVID-19 pandemic).

In addition, all summaries of TEAEs based on “100 subject years” will include EAIR (with 95% CI) and EAER.

The following summaries will be presented for subjects who switched from secukinumab to bimekizumab at Week 48. The analyses will assign AEs according to the AE onset date relative to last secukinumab dose and accounting for approximately 5 times half-life (Onset  $\leq$  140 days from last secukinumab dose or Onset  $>$  140 days from last secukinumab dose):

- Incidence of TEAEs Overview
- Incidence of TEAEs per 100 Subject-Years
- Incidence of Serious TEAEs per 100 Subject-Years

### 10.2.3 Other Safety topics of interest

The following summaries for AEs of other safety topics of interest will be provided by actual Treatment at the time of the adverse event. The following outputs will be produced separately for the SS for the initial treatment period, for the SS for the Initial and Maintenance Treatment Period, and for the OLS for the Open-Label Extension Period by treatment group (see Section 3.6). No safety topics of interest AE summaries will be produced for the Open-Label Extension 2 treatment period (OLS2).

Similar outputs for hypersensitivity events and hepatic events will also be produced for the Maintenance Treatment Period for the MS.

Additional analyses will be presented for subjects who switched from secukinumab to bimekizumab at Week 48 and the AEs will be assigned according to the onset date relative to last secukinumab dose and accounting for approximately 5 times half-life (Onset  $\leq$  140 days from last secukinumab dose or Onset  $>$  140 days from last secukinumab dose).

Along with the tables described, there will be tables which displays the risk difference and 95% confidence intervals for each of the topics of interest during the Initial Treatment Period (SS) as well as for Initial and Maintenance Treatment Period combined (SS). Corresponding figures (with dot plots) will be prepared.

Listings of all treatment emergent adverse events of other safety topics of interest will be provided separately for the OLE and the OLE2 treatment periods.

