### 2.3.2.2 Initial Treatment Period

During the first 16 weeks of the 48-week double-blind Treatment Period, approximately 700 subjects will be randomized 1:1 to receive the following blinded IMP regimens:

- Bimekizumab 320mg administered sc every 4 weeks (Q4W) (350 subjects)
- Secukinumab 300mg administered sc at Baseline and Weeks 1, 2, 3, and 4 followed by dosing Q4W (350 subjects)

Subjects receiving bimekizumab 320mg will receive placebo sc on Weeks 1, 2, and 3 in order to maintain the blind.

Subjects will be classified as completing the initial treatment period if they complete the Week 16 Visit without early withdrawal from the study or if they start treatment in the maintenance treatment period. The start of the maintenance treatment period marks the end of the initial treatment period.

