### 2.3.2.3 Maintenance Treatment Period

At Week 16 subjects in the bimekizumab 320mg treatment arm will be re-randomized 1:2 to receive bimekizumab 320mg Q4W or bimekizumab 320mg Q8W. To maintain the blind after re-randomization, subjects in the bimekizumab 320mg Q8W treatment arm will receive placebo at Weeks 20, 28, 36, and 44. Subjects in the secukinumab arm will continue to receive secukinumab 300mg Q4W.

Subjects will be classified as completing the maintenance treatment period if they complete the Week 48 Visit without early withdrawal from the study or if they start treatment in the Open-Label period. The start of the Open-Label extension period marks the end of the maintenance treatment period for subjects opting to participate in the OLE period. Otherwise the end of the maintenance period is marked by the Week 48 visit.

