### 10.1.3.2 For subjects who switch from BKZ 320mg Q4W to Q8W at Week 16:

Study medication duration (days)

- Initial Treatment Period (attributed to BKZ 320mg Q4W)
  - Date of last dose in the Initial Treatment Period – date of first dose + 28 days

Note: If date of last dose in the Initial Treatment Period + 28 days extends to a date beyond the first dose in the Maintenance Treatment Period, then this calculation reverts to:

  - Date of first dose in the Maintenance Treatment Period – date of first dose + 1.
- Maintenance Treatment Period (attributed to BKZ 320mg Q8W)
  - Use the study medication duration algorithm specified for the Maintenance Treatment Period in Section 10.1.2
- Initial and Maintenance Treatment Period (attributed to Total BKZ)
  - Study medication duration in Initial Treatment Period + Study medication duration in Maintenance Treatment Period.

Time at risk (days)

- Initial Treatment Period (attributed to BKZ 320mg Q4W)
  - Date of first dose in the Maintenance Treatment Period - date of first dose + 1 day.
- Maintenance Treatment Period (attributed to BKZ 320mg Q8W)
  - Use the time at risk algorithm specified for the Maintenance Treatment Period in Section 10.1.2
- Initial and Maintenance Treatment Period (attributed to Total BKZ)
  - Use the time at risk algorithm specified for subjects who do not switch study treatments in Section 10.1.3.1

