## 10.2 Adverse events

An AE is any untoward medical occurrence in a subject or clinical investigation subject administered a pharmaceutical product that does not necessarily have a causal relationship with this treatment. An AE can therefore be any unfavorable and unintended sign (including an abnormal laboratory finding), symptom, or disease temporally associated with the use of a medicinal (investigational) product, whether or not related to the medicinal (investigational) product.

Adverse events will be coded according to the MedDRA. AEs will be allocated to the respective randomized treatment arm. For subjects who switch treatment at Week 16, Week 48 or (on or after Week 64), any adverse events that occur after initiation of the new treatment are attributable to the new treatment. If an adverse event occurs on the date of a treatment switch, the event is attributed to the original treatment. The only exception to this is if the AE fulfills any of the criteria specified below:

- Events that fulfill the anaphylaxis criteria for acute events
- Events that fulfill the hypersensitivity criteria
- Events with an HLT of “Administration site reactions NEC”
- Events with an HLT of “Injection site reactions”

For results disclosure on public registries (eg, ClinicalTrials.gov), treatment-emergent adverse events and treatment-emergent serious adverse events will be published.

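### For most safety topics the only double-blind table with both Q4W and Q8W rates puts everyone's first 16 weeks in the Q4W column, so dose interval is mixed with time on treatment

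*SAP*

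**What the plan says.** All bimekizumab subjects start on Q4W (SAP 2.3.2.2). At Week 16 they "will be re-randomized 1:2 to receive bimekizumab 320mg Q4W or bimekizumab 320mg Q8W" (2.3.2.3).

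Section 10.2.3 states that the topic summaries "will be provided by actual Treatment at the time of the adverse event". For the double-blind phase it lists two tables per topic, both on the SS: Initial, and Initial and Maintenance combined. It then adds: "Similar outputs for hypersensitivity events and hepatic events will also be produced for the Maintenance Treatment Period for the MS". No other topic gets a maintenance-only table in that section.

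Two rules decide what goes into each dose column of the combined table:

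- **Time at risk.** For subjects who move to Q8W at Week 16, Section 10.1.3.2 assigns the first period to Q4W and the second to Q8W, and also defines a Total BKZ attribution.
- **Events.** At a switch, Section 10.2 says "any adverse events that occur after initiation of the new treatment are attributable to the new treatment". Earlier events stay with Q4W.

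For general adverse events the plan does more. Section 10.2.2 also produces the TEAE overview, TEAEs, serious TEAEs, TEAEs leading to discontinuation and TEAEs by decreasing frequency "for the MS for the Maintenance Treatment Period".

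**The concern.** The re-randomisation at Week 16 creates two groups that differ only in dose interval and are followed over the same weeks. A table on the MS reports the topics by those groups.

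The combined table does not. Its Q4W column contains early treatment time from every bimekizumab subject, including those later assigned to Q8W, while the Q8W column contains none. Subjects who stop before Week 16 can appear only under Q4W, so the columns also differ in early dropout. If the rate of a topic changes with time on treatment, the change appears as a difference between dose intervals.

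These are the events the SAP singles out for special reporting. A reader who wants to know whether the longer interval alters, say, the fungal infection rate will look at the two adjacent columns, and the plan offers no other double-blind topic table showing both.

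**Working it through.** The SAP gives no figure on this point to reproduce. Its only power calculation (2.4) concerns PASI100 at Week 16 and plays no part here.

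**Which tables show both regimens**

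- Initial table (SS): all bimekizumab subjects are on Q4W, so there is no Q8W rate.
- Combined table (SS): both Q4W and Q8W. Section 10.1.3.2 defines separate attributions, and 10.2.3 has no restriction to Total BKZ such as 10.2.2 places on its antibody-status table.
- Maintenance table (MS): hypersensitivity (10.2.3.7) and hepatic events (10.2.3.8) only. The six sections 10.2.3.1 to 10.2.3.6 have no dedicated output. Serious infections within 10.2.3.1 are an exception, because they are read from the SAE table, which has an MS version.

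**Inputs from the SAP:** 350 subjects start bimekizumab (2.3.2.2); the split at Week 16 is 1:2 (2.3.2.3); the periods last 16 and 32 weeks (2.3.2).

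**Person-time with full follow-up**

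- Q4W, Weeks 0-16: 350 × 16 = 5600 person-weeks (107.3 PY)
- Q4W, Weeks 16-48: 350/3 × 32 ≈ 3733 person-weeks (71.5 PY)
- Q4W column in total: about 9333 person-weeks, and 5600/9333 = 60% of it is from Weeks 0-16
- Q8W column: 350 × 2/3 × 32 ≈ 7467 person-weeks (143.1 PY), none from Weeks 0-16

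**Apparent rate ratio with no dose effect.** Let λ be the rate after Week 16 on either regimen and kλ the rate before it. The Q4W column then shows λ(0.6k + 0.4), the Q8W column shows λ, and the ratio is 0.6k + 0.4. The value of k is an assumption, so a range is shown:

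- k = 0.5: 0.6 × 0.5 + 0.4 = 0.70
- k = 1: 1.00
- k = 1.5: 1.30
- k = 2: 1.60
- k = 3: 2.20

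**Sensitivity (assumed values)**

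- If 5-10% leave before Week 16, the early share is about 61% and the ratio at k = 2 is about 1.61.
- If time is counted to first event, as the EAIR does, late rates of 5, 10 and 25 per 100 PY give ratios of 1.61, 1.62 and 1.64 at k = 2.

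**Comparison on the MS.** Both columns cover Weeks 16-48, so with no dose effect the expected ratio is 1.00 whatever k is.

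**The case against.** **No Q4W-versus-Q8W safety contrast is planned.** This stands. The Q4W-versus-Q8W objective in 2.1.3 concerns maintenance of efficacy. The safety contrasts the SAP computes are bimekizumab-minus-secukinumab risk differences (10.2.1, 10.2.3). A reader might infer an inflated false-positive rate, but the documents specify no test of Q4W against Q8W for safety, so no such rate attaches to the plan.

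**The direction is not known.** This also stands. A reader might infer that the layout always flatters Q8W. The SAP gives neither topic rates nor their course over time: at k = 1 there is no distortion, and below 1 it runs against Q8W.

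**The Initial table already isolates Weeks 0-16.** It does, and setting it beside the combined table would reveal a change over time. Event counts and time at risk for maintenance Q4W could be approximated by subtraction. But the SAP does not plan this, EAIR subject counts do not subtract, and events of early discontinuers after Day 112 enter the combined table but not the Initial one (10.1.1, 10.2.2).

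**General MS tables cover much of the ground.** In part. The secondary safety variables in 2.2.3.1 all have MS versions, and single PT or HLT rows for fungal infection and neutropenia can be read there. Grouped topic totals, SMQ totals and adjudicated totals cannot.

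**MS tables would be sparse for rare topics.** True. At an assumed 1 per 100 PY one would expect about 0.7 events on Q4W and 1.4 on Q8W. The commoner topics gain most.

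**Timing.** Section 9 describes the Week 48 interim in the past tense, so added tables would follow that analysis. This calls for labelling them as added by amendment; it is no reason to omit them.

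**Conclusion.** The point holds as a gap in descriptive reporting. For the topics in 10.2.3.1 to 10.2.3.6 other than serious infections, the only planned double-blind topic table with both regimens mixes dose interval with time on treatment. The 60% share follows from the planned numbers with full follow-up. The apparent ratio depends on k: 1.3 to 1.6 for k between 1.5 and 2, none at k = 1, and 0.7 at k = 0.5.

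No endpoint, formal test or planned bimekizumab-versus-secukinumab contrast is affected. A reader might also infer that the Q4W and Q8W columns should come out of the combined tables. That does not follow: their attribution is defined in 10.1.3.2, and the columns are harmless once the maintenance-period tables exist and the reader is pointed to them. The change is worth making because it reports the topics by the groups the trial re-randomises, at little cost.

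**What to change.** In 10.2.3, extend the sentence on hypersensitivity and hepatic events along these lines: *For every safety topic of interest, the same outputs will also be produced on the MS for the Maintenance Treatment Period, by bimekizumab Q4W, bimekizumab Q8W and secukinumab.* Add a footnote to the combined-period topic tables saying that the Q4W column includes Weeks 0-16 of all bimekizumab subjects and that Q4W versus Q8W should be read from the MS tables. Leave the combined-table columns as they are.

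Maintenance time at risk is already defined in 10.1.2 and the output is already planned for two topics, so the work is SAP wording and existing shells run on the MS. The cost is a few more tables, with small counts for rare topics because only about 72 PY on Q4W and 143 PY on Q8W are available.
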